Visit 3, part 2: Participants return to pediatric CTRC and will have their blood glucose concentrations clamped in the hyperglycemic range. Participants will also undergo iohexol and PAH clearance studies, in addition to 4-hour urine collection for album excretion rate (AER) and albumin to creatinine ratio (ACR). Upon completion of visit 2, participants will be provided with a study meal (lunch). This concludes the study. Total duration 6 hours.

A. Outcome Measure(s):

Aim 1:

- Renal oxygenation (R2*) by BOLD-MRI
 - Before and after Lasix
- Renal perfusion by pCASL MRI

Aim 2:

- GFR by iohexol clearance
- ERPF by PAH clearance
- Tubular injury markers (e.g. NGAL, KIM-1, IL-18, MCP-1, YKL-40)

| Table 2: Eligibility Criteria | | |
|------------------------------------|--|--|
| Inclusion criteria | Exclusion criteria | |
| Antibody+ T1D with <10 yr duration | Severe illness, recent DKA | |
| Age 12-21 years BMI ≥ 5%ile | eGFR <60ml/min/1.73m ² or creatinine > 1.5mg/dl or history of ACR≥300mg/g | |
| Weight<350 lbs and > 57 lbs. | ACE inhibitors, angiotensin receptor blockers (ARB), diuretics, sodium-glucose co-transport (SGLT) 2 or 1 blockers, daily NSAIDs or aspirin, sulfonamides, procaine, thiazolesulfone or probenecid, atypical antipsychotics and steroids | |
| Previous exposure to caffeine | Tachyarrhythmias, ADHD, tremors, tics, Tourette's, arrythmias, insomnia and overactive bladder Anemia or allergy to shellfish or iodine | |
| HbA1c <12% | Pregnancy or nursing MRI scanning contraindications (claustrophobia, implantable devices, >350 lbs) | |

B. Description of Population to be Enrolled:

Study Design and Research Methods

Study Diet: Participants will be instructed to follow a study diet 3 days prior to visit 2 (CASPER #17-0820), and between visit 2 and visit 3 (COFFEE #18-1874). The diet will be composed of 45% carbohydrates, 30% fat, 25% protein, goal of 3.45g of salt/day and will have no caffeine (besides what is provided in the cold brew), no decaffeinated coffee, regular soda or syrup, no candy as in our previous studies (58, 59)), as diet affects renal function.

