Potential scientific problems: In any clinical study, unforeseen human factors provide challenges. We have experience with hyperglycemic clamps, iohexol and PAH clearance studies and MRI methods in youth with T1D and have already obtained preliminary data. We anticipate an increase in renal oxygenation due to decreased renal oxygen consumption with preserved GFR and ERPF in response to coffee therapy. In addition, we expect decreased plasma concentration of tubular injury markers in response to coffee therapy. Clearance of PAH is the gold standard method to measure ERPF, and GFR by iohexol clearance is more accurate and precise than eGFR. Importantly, iohexol and PAH clearances do not interfere with the assessment of insulin sensitivity during a hyperglycemic clamp. Mild hyperglycemia (~ 190mg/dl) during the GFR measurements and a salt replete and protein controlled diet are critical strengths as severe hyperglycemia acutely increases GFR, and salt and protein intake influence intrarenal hemodynamics (97). Furthermore, mild hyperglycemia allows us to quantify intrarenal hemodynamic function in a glycemic milieu similar to their native pathophysiology. In contrast, a hyperinsulinemic-euglycemic clamp would render the participants completely normoglycemic, which does not reflect their usual glycemic environment, and expose them to high concentrations of insulin which may interfere with the assessment of their intrarenal hemodynamic function. Based on our preliminary work, we expect the 2 renal sequences (BOLD and ASL) to be completed within 60 min. In our other studies we have had adolescents with T1D, T2D and without diabetes undergo similar MRI procedures lasting 120 min, indicating that recruiting and tolerability in youth for such procedures are feasible. Our research MRI is equipped with in-MRI movie-viewing with noise-cancelling headphones and thus is very tolerable to youth. The participant will be monitored by heart rate, blood pressure, and oxygen saturation measurements, and will be able to communicate with the MRI technician and investigator immediately outside of the scanner. As BOLD is potentially influenced by O₂ delivery (ERPF) and O₂ consumption (tubular Na transport accounts a majority of renal O₂ consumption (103)) we will control for ERPF and fractional excretion of sodium (FeNa). We will perform the MRI after the clamp to remove the effects of acute variations in glycemia on RPF. Participants on medications that might alter O₂ delivery and/or consumption, e.g. angiotensin-converting enzyme inhibitors (ACE-I), angiotensin receptor blockers (ARBs) and diuretics will be excluded.

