Evidence of Benefit to Society: The importance of the knowledge gained from this protocol is high, since DKD is very prevalent in T1D and increases the risk of death from CVD and shortens lifespan. In fact, T2D in youth is increasing in prevalence in parallel with the obesity epidemic. In the United States, almost half of patients with renal failure have DKD. Despite the high prevalence and gravity of DKD in youth onset T1D, widely effective therapeutic options are lacking. Diabetes mellitus is the third most prevalent severe chronic disease of childhood. DKD remains a leading cause of morbidity and mortality, and a major risk factor for CVD in diabetes. Although data to guide care of DKD in adults with diabetes are limited, even less data exist regarding the antecedents of DKD in youth with diabetes. Yet, these antecedents of adult DKD are present in childhood, data to inform clinicians as to treatment in this high-risk population are of great public health importance. In our novel and innovative proposal, we postulate that coffee will decrease renal oxygen consumption, thereby improving renal oxygenation without impairing GFR and ERPF. Knowledge gained from this proposal will provide new information about the effects of coffee on renal energetics and intrarenal hemodynamic function in T1D. The investigative team is also unique in being one the few groups skilled in performing both gold standard renal physiology studies and advanced MRI evaluation in youth with T1D.

G. Data Analysis Plan (formulated with biostatistician [name] PhD):

Aim 1-2 Power calculations, statistical analysis, rigor and reproducibility: For this initial pilot and feasibility trial, we plan to recruit 10 youth. Power calculations are based on paired *t*-tests. A sample size of 10 provides 80% power to detect a mean paired difference of 0.44 SD for renal oxygenation and tubular injury markers. The following variables will be considered for inclusion in models as confounders: response: age, sex, ethnicity, T2D duration, HbA1c, BP, LDL-C and FeNa. We will use paired *t*-test and McNemar's test in addition to multivariable linear models of the change in each outcome, adjusted for potential confounders. This is a pilot and feasibility study and the data should be considered hypothesis generating. We acknowledge that we may be underpowered for multivariable modeling, and our primary analyses will be unadjusted.

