Renal Volume: Using 3D Slicer (SPL, Harvard Medical School, MA), the semi-automated segmentation of kidneys will be conducted initially with a thresholding procedure. Manual editing will then be performed to refine the segmentation of bilateral kidneys by placing straight lines at the convex level to separate the right kidney from liver and to remove bilateral ureters from the kidneys. This editing process will need to be performed on few contiguous slices with limited human interaction. The kidney volume will then be computed as the number of voxels within one kidney multiplied by the voxel size.

BOLD MRI: Regions of interest (ROI) analysis for BOLD MRI will be performed on a Leonardo Workstation (Siemens Medical Systems, Germany). Typically, 1 to 3 regions in each, cortex and medulla, per kidney per slice will be defined leading to a total of about 10 ROIs per region (cortex and medulla) per subject. The mean and standard deviation of these 10 measurements will be used a R_2^* measurement for the region, for the subject and for that time point. Additionally, two ΔR_2^* s will be calculated as defined below:

 ΔR_2^* (medulla, furosemide) = R_2^* (medulla, pre-furosemide) - R_2^* (medulla, post-furosemide);

 ΔR_2^* (cortex, medulla) = Baseline R_2^* (medulla) – Baseline R_2^* (cortex).

ASL MRI: ROI analysis will be used to estimate ΔM (difference in signal intensity between non-selective and selective inversion images). Using the same ROI, M₀ will be estimated from the proton density image. T₁ measurements from the same ROI will be obtained by fitting the signal intensity *vs.* inversion time data as described previously (104) using XLFit (ID Business Solutions Ltd., UK) or T₁ maps created using MRI Mapper (Beth Israel Deaconess Medical Center, Boston). Partition coefficient will be assumed to be 0.8 ml/gm (105, 106). These values will then be used to estimate regional blood flow.

For data analyses, all MRI markers will be measured for each kidney (left and right) for each subject and these two measurements for each specific MRI marker would be averaged to generate a summary measurement per subject for further statistical analysis. BOLD MRI measurements will be performed before and after administration of furosemide and the relative value (pre minus post) will be reported. The final averaged value will be analyzed statistically.

Summary of MRI Parameters:

| Renal Volume: | Left kidney volume (LKV), Right kidney volume (RKV) |

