|--------------------|--|
| Diffusion Imaging: | ADC _{Left} (cortex), ADC _{Left} (medulla), ADC _{Right} (cortex), ADC _{Right} (medulla) |
| BOLD MRI: | R ₂ *(cortex) ^{pre} Left, R ₂ *(medulla) ^{pre} Left, R ₂ *(cortex) ^{pre} Right, R ₂ *(medulla) ^{pre} Right |
| | $R_2^*(cortex)^{pos}_{Left}$, $R_2^*(medulla)^{pos}_{Left}$, $R_2^*(cortex)^{pos}_{Right}$, $R_2^*(medulla)^{pos}_{Right}$ |
| | Pre – pre-furosemide; pos – post-furosemide |
| ASL MRI: | flow _{Left} (cortex); flow _{Right} (cortex) |

Data Management:

Data Entry

Data will be entered from paper forms. Once forms are completed, verified and corrected for inconsistencies, they will be manually entered using a HIPAA compliant, Red Cap database system.

Edit Checks

Computerized data validation routines will be used to enhance data quality and verify the accuracy of data within predefined value ranges. These checks include but are not limited to: (a) initial screening of data, using logic and range checks built into data entry screens; (b) cross-form functional and consistency checks; and (c) edits assessing the serial integrity of data.

Disaster Recovery

Routine data backup will occur on data in conjunction with the children's hospital secure server and Redcaps.

Security and Confidentiality

All hard copy forms will be de-identified with a study number and filed in a locked cabinet, to which only the investigators will have access. Standard protection against computer hackers is implemented. Recovery from natural disasters (water, fire, or electrical) can occur through the ability to reconstruct both the database management system and the data from nightly backups.

H. Summarize Knowledge to be Gained:

The innovative and novel pilot and feasibility trial aims to define the effects of coffee therapy on renal energetics and intrarenal hemodynamic function in youth with T1D. Carefully designed human studies, like the one proposed in this application, are needed to advance our understanding of the pathophysiology driving early DKD and direct the development of new therapeutic strategies to impede the development of DKD. Finally, the findings of this project could also inform other acute and chronic kidney disease conditions. The data obtained from this project will help delineate which renal processes are influenced by coffee consumption. The results and techniques from this project will be used to direct future collaborative clinical trials between Drs. [name] and [name].

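### Does the plan need to name a single BOLD value as the test of H1, given that it says the pre-minus-post furosemide difference is what gets reported?

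*Combined protocol and SAP*

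**What the plan says.** The specific aims (SA1, H1) predict that coffee improves renal oxygenation and perfusion. Section A, Outcome Measure(s), lists for Aim 1 "Renal oxygenation (R2*) by BOLD-MRI", measured before and after the diuretic. Both imaging visits scan in both states.

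Section G, Data Analysis Plan, has four relevant elements:

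- The BOLD MRI paragraph forms an R2* value from about 10 regions of interest, "for the region, for the subject and for that time point". It then adds two differences: medulla pre minus post furosemide, and baseline medulla minus baseline cortex.
- The data-analysis paragraph says "all MRI markers will be measured for each kidney (left and right) for each subject" and averages left and right into one summary per subject for statistical analysis. It continues: "BOLD MRI measurements will be performed before and after administration of furosemide and the relative value (pre minus post) will be reported". It ends: "The final averaged value will be analyzed statistically".
- The Summary of MRI Parameters lists R2* by region, kidney and furosemide state, with the key "Pre – pre-furosemide; pos – post-furosemide". No difference appears there.
- The power statement reads "A sample size of 10 provides 80% power to detect a mean paired difference of 0.44 SD for renal oxygenation and tubular injury markers". It treats oxygenation as one quantity and does not say which. The same paragraph calls the study hypothesis generating and makes the unadjusted analyses primary.

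**The concern.** A level and a furosemide response are different quantities, and one can move without the other. If coffee lowered R2* by the same amount before and after furosemide, the pre-minus-post difference would show nothing. An analyst who took the reporting sentence as the rule for H1 would then miss an effect on oxygenation itself.

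The opposite reading carries a different risk. With four levels and two differences available and none ranked, a favourable one could be picked after the data are seen.

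The favourable direction of R2* is not written down as an analysis rule either. Section III, Preliminary Studies, reports lower cortical oxygenation in CKD as 18.0 versus 20.6 s⁻¹, which taken literally links a smaller number with worse oxygenation. The pre-minus-post sign convention may hint at an expected fall after furosemide. Because section II says the pilot is to direct a larger trial, an unsettled choice could be carried forward.

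**Working it through.** **1. Is there a contradiction?** Setting the places side by side:

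| Place | BOLD quantity |
|---|---|
| H1 | renal oxygenation, no variable named |
| Section A, Aim 1 | R2*, both furosemide states |
| Section G, BOLD MRI | R2* by region and time point, plus two differences |
| Section G, data-analysis paragraph | all MRI markers averaged over kidneys and analysed; pre minus post reported |
| Summary of MRI Parameters | per-kidney levels |

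The differences are introduced as additions to the levels. The parameter table lists per-kidney measured values, so derived quantities need not appear in it. Nothing says that only the difference is analysed. The candidates, after averaging the kidneys, are 2 regions × 2 states = 4 levels, plus 2 differences = 6. A cortical pre-minus-post, which the reporting sentence would allow, makes a seventh. This is an unranked list, not a conflict.

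**2. The plan's own power figure.** With n = 10, a two-sided 0.05 test (assumed; the plan states neither) and 0.44 read as SDs of the paired change, the noncentral t gives 23.8%, not 80%. Power of 80% needs 0.996 SD. That is a separate question. The figure names no BOLD variable and so cannot show which one was meant.

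**3. What if the difference alone tested H1?** Let f be the share of the pre-furosemide effect that persists after furosemide, and r the correlation of the pre and post changes. The documents give neither. Assume equal variances and an effect with 80% power on the level. The standardised effect on the difference is

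0.996 × (1 − f) / √(2(1 − r)).

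For example, f = 0.5 and r = 0.5 give 0.996 × 0.5 / 1 = 0.498, hence 29% power.

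| f | r = 0.3 | 0.5 | 0.7 | 0.8 | 0.9 |
|---|---|---|---|---|---|
| 0.25 | 43% | 56% | 77% | 91% | 99.7% |
| 0.5 | 22% | 29% | 44% | 60% | 88% |
| 0.75 | 9% | 11% | 15% | 20% | 35% |
| 1 | 5% | 5% | 5% | 5% | 5% |

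The two choices break even at f = 1 − √(2(1 − r)): never at r = 0.3, then 0, 0.23, 0.37 and 0.55. Below that f the difference has more power than the level; above it, less. The grid runs from 5% to 99.7% on two unknown inputs, so it does not show that either choice is better.

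**4. What if any of the six could be claimed?** A simulation of null trials with n = 10 used four exchangeable changes with correlation r from 0.3 to 0.9, plus the two defined differences:

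- at least one of six with p < 0.05 in either direction: 18-23%;
- at least one of six significant in the favourable direction (taken as a fall in each value): 9-13%;
- either of the two pre-furosemide regions: 7-10% in either direction, 4-5% in the favourable one.

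H1 is directional, so the favourable-direction figures are the relevant ones. A single two-sided 0.05 test gives 2.5% there.

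**The case for a change.** The strongest case for a change is that it would cost a sentence or two and no extra scans. The plan states a directional hypothesis, a test and a power, yet never says which BOLD value carries them. The only sentence about reporting names the difference, so publication of the levels is not promised. The direction is left to cues that do not clearly agree, and the acquisition table in section IV allows either a T2* or an R2* map depending on software version; these are reciprocals, so their signs reverse.

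Much of this is true. No section ranks the values or states the direction, and writing both down beforehand would be tidy. It does not show that the plan as written would mislead. The levels are defined, averaged and kept for analysis, so a null difference would sit beside them. The direction of R2* belongs to the measurement convention, which the imaging group would settle whatever the results. The section III figures are background and set no rule for this trial.

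Putting the pre-furosemide level first is also not clearly an improvement. The overall hypothesis is better oxygenation through lower oxygen consumption, and section E says "We anticipate an increase in renal oxygenation due to decreased renal oxygen consumption with preserved GFR and ERPF in response to coffee therapy". Section E also notes that BOLD reflects oxygen delivery as well as consumption. If furosemide acts on the sodium transport that the protocol names as the main consumer of oxygen, which the documents do not spell out, the difference is a reasonable index of that mechanism. Naming the level would still leave cortex or medulla to be chosen.

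**Conclusion.** The plan leaves out a detail: it does not name one BOLD value for H1 or its favourable direction. It does not contradict itself, and it does not replace the level with the difference. Analysts can fill the gap sensibly by analysing the regional levels in both states together with the defined differences, as section G already provides.

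The size is modest. With free choice among six values, a false favourable finding would arise in roughly 9-13% of null trials, assuming exchangeable changes with correlations from 0.3 to 0.9. The power loss from relying on the difference applies only to a reading the plan does not impose, and it becomes a gain at high correlation and low persistence. In an uncontrolled study of 10 participants, labelled hypothesis generating and with every component kept, neither risk calls for a change to the plan. The choice of BOLD variable matters more for the larger trial, which can make it with all the pilot's components in hand.
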